## **I. Hypotheses and Specific Aims**

### Hypotheses

- 1) Shingrix (RZV) recipients will have a lower rate of varicella-zoster virus (VZV) DNAemia after a live intradermal (ID) VZV challenge (vOka vaccine) than Zostavax (ZVL) recipients because of higher and/or more rapid VZV-specific T cell responses.
- 2) After a live VZV ID challenge, RZV recipients will have the same rate of VZV DNAemia whether the challenge was performed <1 or >5 years after vaccination; whereas ZVL recipients will have lower rates of VZV DNAemia if they are challenged <1 year after vaccinations compared with >5 years.
- 3) The peak memory VZV and/or gE Th1 responses to RZV mediate protective immune responses conferred by RZV against VZV DNAemia after VZV ID challenge; early responses may also play a role

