### Specific Aims/Study Objectives

**Primary Objective 1.** To compare the rate of vOka DNAemia within 7 days after ID vOka administration in adults who received RZV or ZVL >5y before the challenge.

**Primary Objective 2.** To compare the rate of vOka DNAemia after ID vOka challenge at <1y after RZV or ZVL vaccination and at >5y after vaccination.

**Secondary Objective 3.** To identify the characteristics of the immune responses to RZV that predict the immunologic control of vOka DNAemia after ID vOka challenge at <1y and at >5y after vaccination.

*Note:* This will include studies to further define epitope-specific immune responses, and will measure transcript profile and epigenetic changes in immune cells following vaccination.

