## C. Study Design and Research Methods

### **Part A; Cohorts 1 and 2**

Seventy subjects with documented evidence of a HZ vaccine at least 5 years previously, divided equally between recipients of ZVL (Cohort 1) or RZV (Cohort 2) - 35 in each group - will be enrolled. Participation will consist of 4 visits over the course of 7-10 days in which blood is drawn, a challenge dose of vOka is given, and a skin biopsy is obtained.

ID vOka challenge live attenuated VZV (as 1 dose of licensed ZVL; Zostavax) will be prepared by mixing 0.35 ml of accompanying diluent with the vaccine and injecting 2 side-by-side intradermal doses of 0.125ml each, for a total of 0.25 ml (about  $\frac{3}{4}$  of the normal dosage or 13,857 plaque forming units) intradermally in the non-dominant deltoid region, using a NanoPass MicronJet600 device, on D0. Blood (60 ml) will be drawn prior to vaccination (D0), and at Days 1, 3, and 7. A skin biopsy (4 mm punch biopsy) will be done at the injection site, on the first 20 subjects (up to 25, if replacements needed) in each vaccine group; five each of these 20 will be biopsied on Day 0, 1, 3, or 7 in the order in which the participants enter the study. The Day 0 biopsy will be done on the contralateral arm in the deltoid region prior to vaccination. Initially every subject enrolled will be required to do the biopsy; this is reflected in the consent. The consent form will be amended to remove references to the biopsy procedure once the number of subjects needed for the biopsies is reached.

Subjects in the ZVL group will be offered RZV vaccine (to comply with ACIP recommendations for shingles immunization), to be administered beginning  $\geq$  60 days after Day 0. If subject wishes to receive the RZV vaccine, 2 additional visits will be required at Day 60 and Day 120, increasing the duration of participation up to 4 months. Subjects will not be reimbursed for these visits but will receive the vaccine free of charge.

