##### For analysis of kinetics of DNAemia:

For sample size estimation, we assumed an incidence of viremia of 86% in the ZVL group and a  $\geq 2$ -fold reduction in the RZV group. The 2-fold reduction is a conservative estimate, considering that the efficacy is 2.9-fold higher 5y after RZV vs. ZVL. With 19 participants per group, we have 80% power to detect a 2-fold difference in viremia with  $\alpha=0.05$ . However, a larger sample size is needed to achieve the 2ary objectives. 35 participants per group will allow us to have sufficient power in correlation analyses of our primary outcome measure with 2 measures of the immune responses, which may represent clusters of several analytes that group together using PCA or other dimensionality reduction method. For the primary objective, logistic regression models will be fit using VZV DNAemia defined in Section 13.2. as a dependent variable and vaccine group as the primary independent variable and adjusted for potential confounders such as age at vaccination, age at ID vOka challenge, sex, and/or race as appropriate. For all regression models fit to the data, 95% confidence intervals will be reported based on Wald statistics in conjunction with appropriate asymptotic normal distributional theory. Secondary analyses will include the duration of DNAemia defined as the last day after ID vOka administration when the VZV DNA PCR

Relative change in percentages between groups	Total sample size (50% of total in ZVL group and 50% in SRX group)
50%	70
65%	60
80%	45
90%	25

was positive, the magnitude of VZV DNAemia, defined as the peak viral load, and the occurrence of VZV RNAemia defined as  $\geq 1$  VZV RT-RNA PCR positive result during the first week after the ID vOKA challenge.

For analysis of soluble factors and phenotypic markers:

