With the different biological measurements, the major analytical goal will be to determine biomarkers that serve as intermediates in the pathway between virus challenge with DNAemia. With all the matched measurements (transcriptomic, soluble marker, VZV-CMI T cell responses) on the same subjects, we will use mediation analysis methods (15) in order to evaluate the mediation potential of these markers. As a primary analysis, we will create a composite mediation score based on the following linear combination:  $V_i = \sum_{m=1}^M \beta_m X_{mi}$ , where  $\beta_m$  denotes an association between molecule m with the exposure, and  $X_{mi}$  is the measurement on molecule m for subject i,  $i=1,\dots,n$ . Upon standardizing V, we then can test for mediation using the approach in Vittinghoff et al. (16). Based on the available  $n = 70$ , we performed power analyses based on the Vittinghoff et al. approach to evaluate power for mediation of the composite marker. We assumed that the probability of outcome is 56% based on our preliminary data and that we are testing at a significance level of 0.05. Using the powerMediation package in R (<https://cran.r-project.org/web/packages/powerMediation/index.html>), with the given sample size, we will have at least 80% power of identifying mediating effects of V that

are at least 1.96 on the log odds ratio scale based on the proposed extended Sobel test given in Vittinghoff et al. (16).

Sample size: Sample size is 70. Calculation for predictability of this sample size is described above.

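### Primary Objective 2 (<1y versus >5y) is not tested by the planned model or covered by the sample size, and 35 per cohort cannot support a same-rate conclusion for RZV

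*Combined protocol and SAP*

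**What the plan says.** Under Specific Aims/Study Objectives, Primary Objective 2 is "To compare the rate of vOka DNAemia after ID vOka challenge at <1y after RZV or ZVL vaccination and at >5y after vaccination". Hypothesis 2 gives the expected pattern: for RZV, "RZV recipients will have the same rate of VZV DNAemia whether the challenge was performed <1 or >5 years after vaccination"; for ZVL, "ZVL recipients will have lower rates of VZV DNAemia if they are challenged <1 year after vaccinations compared with >5 years". No equivalence margin is stated, and no size is given for the ZVL change.

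The analysis of DNAemia is in section IV.G. It describes a single logistic regression for the primary objective, in the singular, with "vaccine group as the primary independent variable". Age at vaccination, age at challenge, sex and race are possible confounder adjustments. Wald 95% confidence intervals are promised for every regression model.

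The sizing in the same section concerns RZV against ZVL: "we assumed an incidence of viremia of 86% in the ZVL group", at least a 2-fold reduction with RZV, and 19 per group for 80% power at alpha 0.05. The small table of relative changes is also split between the two vaccines. The move from 19 to 35 per group is justified by correlation analyses for the secondary objectives. Section IV.G closes with "Sample size: Sample size is 70", whereas the Inclusion Criteria list four cohorts of 35, which is 140.

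Biopsies belong to Part A only: "A skin biopsy (4 mm punch biopsy) will be done at the injection site, on the first 20 subjects" of each vaccine group, five each on Days 0, 1, 3 and 7, with the Day 0 biopsy on the opposite arm. The schedules for Cohorts 3 and 4 contain no biopsy.

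**The concern.** A primary objective about change with time since vaccination needs a model in which time since vaccination appears. A vaccine-group coefficient answers Objective 1; it says nothing about Cohort 4 against Cohort 2 or Cohort 3 against Cohort 1. The two age covariates together carry the interval, but they are listed as optional adjustments and neither is named as a test.

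Hypothesis 2 also contains two statements that ordinary significance tests do not deliver. No change for RZV is an equivalence statement and needs a margin and enough precision. The contrast between a waning vaccine and a stable one is an interaction; a significant change in ZVL beside a non-significant change in RZV is not evidence that the changes differ. At stake is the durability conclusion for RZV, for which half of the participants (Cohorts 3 and 4) are enrolled.

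**Working it through.** **1. The plan's own figure.** ZVL 86%, RZV 86/2 = 43%, two-sided alpha 0.05 (sidedness is not stated), power 80%, pooled variance, no continuity correction; mean rate 64.5%.

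n = [1.96·√(2·0.645·0.355) + 0.842·√(0.86·0.14 + 0.43·0.57)]² / 0.43² = 18.2, so 19 per group. The stated figure reproduces. With 35 per group, power for that contrast is 97.8%. Objective 1 is well covered; the gap is confined to Objective 2.

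**2. RZV rates to use.** The documents give no RZV rate directly.
- At least a 2-fold reduction from 86%: at most 43%.
- The 56% overall outcome probability in the mediation paragraph of IV.G, with equal groups and ZVL at 86%: 2·56 − 86 = 26%.
- The 2.9-fold figure, if read as a rate ratio (an assumption): 86/2.9 ≈ 30%, inside that range.

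**3. Precision for RZV >5y minus <1y, 35 per cohort.** SE = √(2p(1−p)/35).
- p = 43%: SE = 0.118, 95% half-width 1.96·SE = 23 points.
- p = 26%: SE = 0.105, half-width 21 points.

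**4. Equivalence power if the true difference is zero** (two one-sided 5% tests; margins assumed). Power = 2Φ(m/SE − 1.645) − 1, or 0 if negative. The smallest margin with 80% power is SE·(1.645 + 1.282). The number needed is 2p(1−p)·(1.645 + 1.282)²/m².

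| | RZV 26% | RZV 43% |
|---|---|---|
| Power, 15-point margin | 0% | 0% |
| Power, 20-point margin | 21% | 4% |
| Power, 30-point margin | 78% | 63% |
| Smallest margin with 80% power | 30.7 points | 34.6 points |
| Needed per cohort, 20-point margin | 83 | 105 |

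A workable margin of 31 to 35 points is not far below the 43-point difference (86 − 43) that the trial assumes between the vaccines.

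**5. Power to detect real RZV waning from 43%** (exact power of the chi-square test, 35 per cohort). Rise to 60%: 27%. To 65%: 44%. To 70%: 62%. To 75%: 79%.

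**6. Power of the vaccine-by-interval interaction.** RZV 43% at both times and ZVL 86% at >5y. The ZVL <1y rate is not in the documents, so it is varied as an assumption. Power = Φ(δ/SE − 1.96).

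For ZVL <1y = 50% on the risk-difference scale: δ = 0.36, SE = √[(0.1204 + 0.25 + 2·0.2451)/35] = 0.157, power 63%. On the logit scale: δ = 1.815, SE = √[(1/0.1204 + 1/0.25 + 2/0.2451)/35] = 0.765, power 66%.

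| Assumed ZVL <1y rate | Risk difference | Logit |
|---|---|---|
| 40% | 84% | 82% |
| 50% | 63% | 66% |
| 56% | 48% | 54% |
| 65% | 27% | 34% |

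**7. Biopsy imbalance.** Five on Day 1 plus five on Day 3 gives 10 of 35 per Part A cohort with challenge-site skin removed before the Day 7 blood draw, and none in Part B. Leaving those 10 out changes the SE by √[(1/25 + 1/35)/(2/35)] = 1.095, about 10%.

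**The case against.** The strongest reply is that the objective itself says only compare; the same-rate wording is a hypothesis, and nothing in the documents says that a non-significant RZV result will be read as equivalence. The plan also promises 95% confidence intervals for its regression models. This stands, so the point is what the data could support, not a forecast of what will be reported. A reader might infer that the trial would probably declare durable RZV control even after waning. The documents do not support that, and the chance of missing a change depends on its size, as step 5 shows. The promised intervals do not close the gap either, because no model produces one for the interval contrast.

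Other stronger readings also fail:
- **No sample size for Objective 2.** Cohorts 3 and 4 are each fixed at 35. What is missing is a justification for this contrast.
- **Both primary objectives are tested at 0.05 without order.** Alpha 0.05 is attached to the RZV-versus-ZVL power statement and to mediation, and 0.05 is the false discovery rate for gene expression. No level is given for Objective 2, so the order is unstated and no more can be said.
- **Biopsy hides waning.** The imbalance is real, but no passage supports a size or direction of effect, and DNAemia already present by the biopsy day cannot be prevented by it.

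It may also be said that 43% is a ceiling. At a true RZV rate of 10% or 5%, the margin with 80% power would fall to about 21 or 15 points. That is correct, but the documents assume no such rate. Finally, the RZV >5y population is scarce by the protocol's own account, so a larger Cohort 2 is not a realistic demand. That argues for estimation, not for leaving the claim as it is.

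**Conclusion.** The point holds. As written, the primary model does not test Primary Objective 2, and no power, precision or margin is stated for it. At RZV rates of 26% to 43%, 35 per cohort gives a 95% CI of about ±21 to ±23 points. Equivalence at a 20-point margin would be shown in 21% to 4% of trials, and at 30 points in 78% to 63%. A rise from 43% to 60% or 65% would be detected with 27% or 44% power. A non-significant RZV comparison could not carry the same-rate statement.

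These figures rest on the RZV range inferred from the plan, on margins that are assumptions, and on no losses from the 35; losses would lower every power. The interaction's power cannot be given as one number, because the ZVL <1y rate is not in the documents. The biopsy difference is a matter for a sensitivity analysis only.

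**What to change.** 1. Fit one logistic model to all four cohorts with vaccine, interval (<1y or >5y) and vaccine-by-interval terms, plus age at challenge and sex from the planned covariates. Leave out age at vaccination, since the two ages together determine the interval. Name the interaction as the direct test that change over time differs between the vaccines. A significant interaction would still not show that RZV is unchanged.
2. Report the RZV >5y minus <1y risk difference with its 95% CI. Reword the RZV part of Hypothesis 2 as an estimation statement with the expected precision of about ±21 to ±23 points. Claim equivalence only within a margin fixed and justified beforehand.
3. State that the interaction's power depends on the ZVL <1y rate, with the range in step 6: from 82–84% if that rate is 40% down to 27–34% if it is 65%.
4. State the order of the two primary tests, Objective 1 first, and bring the closing sample size of 70 into line with the four cohorts of 35.
5. As a sensitivity analysis, repeat Objective 2 without the 10 participants per Part A cohort biopsied at the challenge site on Day 1 or 3, and claim no size or direction of biopsy bias beforehand.

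The cost is SAP and hypothesis wording, a little more analysis and a more modest claim about RZV. The sensitivity analysis has an SE about 10% wider. No participants are added.

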### Specific Aims/Study Objectives

**Primary Objective 1.** To compare the rate of vOka DNAemia within 7 days after ID vOka administration in adults who received RZV or ZVL >5y before the challenge.

**Primary Objective 2.** To compare the rate of vOka DNAemia after ID vOka challenge at <1y after RZV or ZVL vaccination and at >5y after vaccination.

**Secondary Objective 3.** To identify the characteristics of the immune responses to RZV that predict the immunologic control of vOka DNAemia after ID vOka challenge at <1y and at >5y after vaccination.

*Note:* This will include studies to further define epitope-specific immune responses, and will measure transcript profile and epigenetic changes in immune cells following vaccination.

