## **IV. Research Methods**

### **A. Outcome Measures/Study Endpoints**

Primary Endpoint - Rate of VZV DNAemia after ID vOka challenge.

Secondary Endpoint – Duration and magnitude of VZV DNAemia and rate of VZV RNAemia. VZV- and gE-specific T cell and other immune cell responses in blood and at the site of ID vOka challenge; cytokines levels in blood and at the site of ID vOka inoculation; transcriptomics of immune cells in blood and skin biopsies; immunohistochemistry of skin biopsies of the ID vOka challenge.

Exploratory Endpoint –After RZV: Tetramer analysis of the T cell responses; T cell epigenome.

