### **Part B; Cohorts 3 and 4 – No Previous HZ vaccine**

Part B measures VZV DNAemia and systemic VZV-specific immune responses after ID vOka challenge in individuals who received HZ vaccines 6 months prior to the injection.

**Cohort 3** (n=35) subjects will be vaccinated with ZVL at enrollment; blood will be obtained at Days 0, 1, 3, 7 and 30 days after. Five - six months after receiving ZVL subject will be challenged with vOka administration (as described in Part A) followed by visits 1, 3, and 7 days later at which blood is drawn. Total of 9 to 11 visits.

These subjects will also be offered RZV vaccine (to comply with ACIP recommendations for shingles immunization) to be administered  $\geq$  60 days after vOka challenge. If subject wishes to receive the RZV vaccine, 2 additional visits will be required 2 beginning 2 months after Visit 6, increasing the duration of participation up to 10 months. Subjects will not be reimbursed for these visits but will receive the vaccine free of charge.

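### The DNAemia endpoint has no single observation window: the last draw may fall on Day 10 after challenge in Cohorts 1, 2 and 4 but on Day 17 in Cohort 3, so the ZVL <1y versus >5y contrast rests on unequal ascertainment of unknown direction

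*Combined protocol and SAP*

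**What the plan says.** **Endpoint.** Primary Objective 1 (Specific Aims/Study Objectives), which concerns Cohorts 1 and 2, is "To compare the rate of vOka DNAemia within 7 days after ID vOka administration in adults who received RZV or ZVL >5y before the challenge". By contrast, Primary Objective 2, which brings in Cohorts 3 and 4, is "To compare the rate of vOka DNAemia after ID vOka challenge at <1y after RZV or ZVL vaccination and at >5y after vaccination", with no time limit. Section IV.A has none either: "Primary Endpoint - Rate of VZV DNAemia after ID vOka challenge". In Section IV.G, "logistic regression models will be fit using VZV DNAemia defined in Section 13.2. as a dependent variable", but no section in the available text bears that number. The secondary RNAemia endpoint in the same section does have a limit, at least one "VZV RT-RNA PCR positive result during the first week after the ID vOKA challenge".

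**Sampling.** The Schedules of Events in Section IV.C place the last post-challenge draw at Day 7 (+3) in Cohorts 1 and 2, Day 247 (+3) after a Day 240 (+14) challenge in Cohort 4, and Day 157 (+10) after a Day 150 (+44) challenge in Cohort 3. Cohort 3's middle draw is Day 153 (+2); the corresponding draw in the other cohorts has no window. The Part A text agrees with its table: "Participation will consist of 4 visits over the course of 7-10 days". The Cohort 3 text does not. It has the challenge "followed by visits 1, 3, and 7 days later at which blood is drawn", with no tolerance.

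**Hypothesis at stake.** Hypothesis 2 predicts that "ZVL recipients will have lower rates of VZV DNAemia if they are challenged <1 year after vaccinations compared with >5 years".

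**The concern.** Each last-draw window runs forward only, so any use of the permitted tolerance takes the sample outside the 7 days named in Primary Objective 1. With three post-challenge draws and a binary endpoint, the last draw can decide a participant's status. The plan does not say whether a positive result on Day 9 counts, or what a negative result on Day 15 shows about Day 7.

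This matters most for the ZVL arm of Primary Objective 2. Cohort 3 (<1y) may be sampled up to 7 days later than Cohort 1 (>5y), and these are the two cohorts that Hypothesis 2 expects to differ. Adjusting for age, sex and race, as Section IV.G proposes, does not correct a difference in when participants were observed. While the counting rule is open, it could also be chosen after the results are known.

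The duration endpoint, defined as the last positive day, has the same weakness because its maximum depends on the cohort.

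**Working it through.** **1. Latest permitted draw, in days after a challenge on the nominal day** (Schedules of Events, Section IV.C)

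| Cohort | Middle draw | Last draw | Range of last draw |
|---|---|---|---|
| 1 and 2 | Day 3 | 7 + 3 = 10 | 7 to 10 |
| 4 | 243 − 240 = 3 | 247 + 3 − 240 = 10 | 7 to 10 |
| 3 | 153 + 2 − 150 = 5 | 157 + 10 − 150 = 17 | 7 to 17 |

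The duration endpoint can therefore reach 17 days in Cohort 3 but only 10 in Cohort 1.

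**2. Anchor of the windows.** Follow-up in Cohorts 3 and 4 is printed in study days, while the challenge itself may move.
- Cohort 3: latest challenge 150 + 44 = Day 194; latest printed last draw 157 + 10 = Day 167.
- Cohort 4: latest challenge 240 + 14 = Day 254; latest printed last draw 247 + 3 = Day 250.

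Read literally, the last draw can precede the challenge. The tables make sense only if the windows run from the actual challenge date, and they do not say so.

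**3. The plan's own sample size.** For 86% versus 43%, two-sided 5% and 80% power, the pooled-variance formula without continuity correction gives the stated 19 per group (power 81.8%). The point does not rest on this figure. The 86% and the 35 per cohort are used below.

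**4. Direction.** Suppose the true 7-day rate p is the same in Cohorts 1 and 3. The documents give no PCR positivity by day, so the shares f and g are assumed to lie between 5% and 30%.
- Loss: a share f of Cohort 3 positives is detectable only at Day 7 and is missed. Observed rate = p(1 − f). At p = 86% this is 81.7% to 60.2%, a change of −4.3 to −25.8 points.
- Gain: a share g of Day 7 negatives turns positive later and is counted. Observed rate = p + g(1 − p). At p = 86% this is 86.7% to 90.2%, a change of +0.7 to +4.2 points.
- At p = 56%, the outcome probability used in the plan's mediation power calculation, the changes are −2.8 to −16.8 and +2.2 to +13.2 points.
- The two effects cancel when pf = (1 − p)g, that is g/f = 0.86/0.14 = 6.1, or 0.56/0.44 = 1.3.

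**5. Illustrative size of the loss.** Assume three independent draws with equal sensitivity s.
- 1 − (1 − s)³ = 0.86 gives s = 1 − 0.14^(1/3) = 0.481.
- With two draws only: 1 − (1 − 0.481)² = 0.730.
- With a quarter of third draws lost: 0.75 × 0.86 + 0.25 × 0.730 = 0.828.

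Exact rejection probability of the pooled two-proportion z-test (two-sided 5%, 35 per cohort, Cohort 1 at 86%):

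| Cohort 3 third draws lost | Cohort 3 rate | Rejection |
|---|---|---|
| None | 86.0% | 5.4% |
| One quarter | 82.8% | 6.8% |
| Half | 79.5% | 10.9% |
| All | 73.0% | 26.3% |

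**The case against.** The strongest reply is that a few days after a nominal visit is an ordinary tolerance. Day 7 is the intended draw, the Part A text itself allows for 7 to 10 days, and one sentence could say that a Day 7 (+3) sample counts as Day 7. For Primary Objective 1 this largely stands. Cohorts 1 and 2 share one schedule, so no difference between arms is built in; what remains is an ambiguity and possibly some lost positives. The reply does not cover Cohort 3, whose tolerance is 7 days wider than that of the cohort it is compared with and conflicts with its own description of draws 1, 3 and 7 days after challenge. That description does suggest that follow-up was meant to run from the challenge, which makes the anchoring problem easy to cure but does not remove it from the tables.

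A reader might also infer that the schedule biases the ZVL contrast toward Hypothesis 2. The documents do not support that. It requires late draws to be discarded, or DNAemia to have cleared before them. If any positive up to Day 17 counts, the longer window raises the Cohort 3 rate and works against the hypothesis. Nor does the 7-day limit, as written, govern that contrast: it appears in Primary Objective 1 only.

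Finally, the 26% needs every Cohort 3 third draw to be lost. The +10 is an allowance, and the share of draws that will use it is unknown.

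**Conclusion.** The point holds as a conflict between endpoint and schedule, and as unequal ascertainment. Followed exactly, the plan observes Cohorts 1 and 3 over periods that may end on Day 10 and Day 17 for the same binary primary endpoint, with no window stated for the objective that compares them and no rule for late samples. Only participants whose status depends on the last draw are affected, so positives may be miscounted; it does not follow that they will be. The day counts assume a challenge on the nominal day, or windows that move with the challenge.

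The sign of any bias is open. Its size is known only under assumptions: from negligible when few Cohort 3 draws are late, through about 7% false rejection if a quarter of the third draws are lost, to about 26% in the extreme case of all being lost. These figures rest on independent, equally sensitive draws and an unadjusted test, and they cover the loss direction only. This should be corrected, but it does not undermine Primary Objective 1 as a comparison between arms.

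**What to change.** Reconcile the objectives, the endpoint line in Section IV.A, the Cohort 3 text and the Schedules of Events in Section IV.C, and the analysis text in Section IV.G.

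1. Count every post-challenge draw from the actual challenge date and say so in the tables.
2. Give one DNAemia definition for both primary objectives, with one analysis window per draw in all four cohorts; for example, at least one positive PCR at the Day 1, Day 3 or Day 7 (+3) draw. State the RNAemia and duration endpoints on the same windows.
3. Bring the Cohort 3 sampling windows for the middle and last draws into line with the other cohorts.
4. Treat a draw outside the common window as missing, not as negative. Treat a participant whose in-window draws are all negative and whose last draw is missing as having a missing outcome, and examine both possible values in a sensitivity analysis.
5. Add a sensitivity analysis by actual draw day.

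The cost is mainly wording, with slightly less visit flexibility in Cohort 3 and a few draws treated as missing. The definition should be fixed before PCR results are compared between cohorts.
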